### **7.1.3 Supportive Care/Concomitant Medications**

Supportive measures may include acetaminophen for fevers, meperidine for chills, anti-emetics for nausea and vomiting, normal saline or furosemide to maintain fluid balance/blood pressure/pulmonary function, and electrolyte replacement. Use of G-CSF is permitted as clinically indicated. Refer to [Section 7.3](#) for management of selected toxicities.

Administration of glucocorticoids is prohibited during the TriKE treatment period as the use of systemic steroid medications may result in loss of therapeutic effects of the study drug. They should be avoided except in the event of a severe toxicity.

The potential risk of QT/QTc prolongation is unknown in humans receiving TriKE. Persons with a family history of long QT syndrome, with a QTc interval > 480 msec at screening, or taking concurrent medications known to prolong QT/QTc interval are not eligible for this study. The use of medications known to prolong QT/QTc interval (refer to [Appendix V](#)) are prohibited between screening and the end of treatment visit if at all possible.

The interactions between TriKE and the P450 system are unknown. The IL-15 component may affect substrates of CYP3A4 and CYP2D6 substrates. See [Appendix IV](#) for a list of drugs which may be affected. Patients with unexpected toxicity should have a review of their con-meds to determine whether there are any potential interactions. The PI or treating physician should consider discontinuing these medications as clinically indicated.

All concomitant medications, with a start and stop date must be documented relative to administration of GTB-3550 TriKE.

#### **7.1.4 Dose Modifications**

No individual patient dose modifications are permitted other than as described in [Section 7.3.3](#) for elevated liver enzymes.

#### **7.1.5 Criteria to Continue with GTB-3550 TriKE Block #2 and #3**

A dose limiting toxicity (for any patient, not just dose finding) during the previous block's infusions (defined in [Section 7.2.1](#)) will disqualify a patient from receiving further therapy.

**Disease based treatment decisions:** If after completing Block #1 and Block #2, the patient has clear evidence of disease progression they will be discontinued from study treatment and further treatment with study drug is to be discontinued. Such patients remain fully evaluable for efficacy and toxicity.

To begin a new block, on the day of the planned treatment the patient must:

- not currently meet any disease specific hematologic dose limiting toxicity as defined in [Section 7.2.1](#).
- have an estimated glomerular filtration rate  $\geq 60$  mL/min/1.73 m^2
- have a total bilirubin of  $\leq 1.5$  times the ULN

- have AST and ALT  $\leq$  3 x upper limit of normal, and alkaline phosphatase levels  $\leq$  2.5 x upper limit of normal
- be afebrile (defined as a temperature of  $\leq$  101°F)
- have room air O2 saturation  $\geq$  88%
- have a blood pressure  $\geq$  100/65 mm/Hg
- have no signs or symptoms of infection

If the above criteria is not met, treatment must be delayed for appropriate supportive care and clinical assessment. The study drug may begin the following day, if the above criteria are met and, in the opinion of the clinical provider it is safe to proceed. Otherwise delay 1 week from the planned start and reassess at that time.

Patients unable to begin treatment after a 1 week delay will be permanently discontinued from treatment and followed per [Section 7.6](#).

The start of Block #2 or Block #3 may be delayed for up to 1 week (i.e. start 1 week later than planned) to allow for the resolution of any treatment or non-treatment issues (i.e. URI, UTI, etc.) or for holiday/scheduling issues.

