    - Grade 4 platelet count (<25,000/ $\mu$ L) lasting  $\geq$  29 days from start of cycle in the absence of active MDS/Mast cell disease
    - Any clinically significant bleeding that is not controllable with transfusion support
    - Grade 4 anemia, unexplained by the underlying disease

- Grade 3 infusion related, treatment related reaction including cytokine release syndrome which does not resolve within 72 hours despite best medical management (refer to [Section 10](#) for modified CRS grading)
- Grade 3 or 4 Tumor Lysis Syndrome that does not resolve within 7 days with or without intervention
- Inability to complete at least one block of three 24 hour infusions due to any treatment emergent, treatment related toxicity.

**Maximum Tolerated Dose (MTD)** is defined as the dose level that most closely corresponds to the target DLT rate of 20%.

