### 7.3 Management of Selected GTB-3550 TriKE Toxicities

Throughout the study, the investigator may prescribe any concomitant medications or treatment deemed necessary to provide adequate supportive care. Supportive care may include antibiotics, anti-fungals, analgesics, transfusions, and G-CSF/cytokines.

Note: Any patient experiencing a DLT equivalent toxicity must discontinue treatment per [Section 7.5](#) and is not eligible for retreatment.

Please refer to [Section 9.7](#) for potential toxicities.

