## 7.5 Duration of Study Treatment

Patients will receive one treatment course consisting of three sets (blocks) of four consecutive 24 hour continuous infusions GTB-3550 TriKE unless:

- the patient experiences the equivalent of a dose limiting toxicity (see [Section 7.2.1](#) for definition),
- the patient is unable to start Block #2 or #3 within 1 week of the planned date,
- the patient refuses further treatment,
- **Disease based treatment decisions:** If after completing Block #1 and Block #2, the patient has clear evidence of disease progression they will be discontinued from study treatment and further treatment with study drug is to be discontinued.
- In the opinion of the treating investigator, continuing treatment is not in the best interest of the patient.

For patients discontinuing prior to completing 3 blocks, post-treatment activities at Day 22 and Day 29 are shifted earlier to maintain the timing (i.e. 1 and 2 weeks from the start of the final block).

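### Section 7.1.5 attaches both a permanent stop and a mere delay to the same hematologic DLT, and its block-start line cannot act on neutrophil or platelet counts at planned or once-delayed starts

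*Combined protocol and SAP*

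**What the plan says.** Section 7.1.5 of the combined protocol and SAP holds two rules that refer to DLTs as defined in 7.2.1.

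- **Opening rule.** "A dose limiting toxicity (for any patient, not just dose finding) during the previous block's infusions" is an event that "will disqualify a patient from receiving further therapy".
- **Block-start list.** On the planned day the patient must "not currently meet any disease specific hematologic dose limiting toxicity as defined in" Section 7.2.1. This stands beside renal, hepatic, temperature, oxygen, blood pressure and infection criteria. The list states its own consequence: "If the above criteria is not met, treatment must be delayed for appropriate supportive care and clinical assessment". It continues: "The study drug may begin the following day, if the above criteria are met", provided the clinician judges it safe. Otherwise the wait is 1 week with reassessment. Only a patient who still cannot start after that week is taken off treatment for good.

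Four other places address the same event. The note in 7.3 reads "Any patient experiencing a DLT equivalent toxicity must discontinue treatment per" Section 7.5. Section 7.5 lists, among the reasons a course ends early, that "the patient experiences the equivalent of a dose limiting toxicity". The research table in 8.2 and the note in 10.3 both say that a patient with a DLT may not go on with treatment. None of these four is limited to infusion days, and none makes an exception for a hematologic DLT that clears.

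Section 7.2.1 requires a DLT to be treatment related and lists the hematologic items by disease. For AML they are neutrophils, platelets and uncontrollable bleeding. For MDS/mast cell disease they are the same three plus "Grade 4 anemia, unexplained by the underlying disease". The two count items carry a 29-day minimum measured from the start of the cycle. Bleeding and anemia carry no duration.

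**The concern.** Within one section, the same defined event is first a reason to end treatment and then a reason to wait and try again. The word 'currently' in the list treats a hematologic DLT as a state that may pass before the next dose, whereas the other provisions treat its occurrence as final. Up to 10 sites may take part, so the same patient could be handled differently depending on which line is applied.

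Two things could then depend on the reading. One is exposure, meaning whether the patient receives a further block. The other is membership of the Phase II response count. Section 12.1 replaces patients who stop before completing Blocks #1 and #2, while a patient who is delayed and then completes Block #2 stays in. That count is compared with small cut-offs (3 of 13, then 10 of 30).

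There is also a second, separate defect. The list appears to check hematologic status at each block start, but the 29-day minimum means it cannot respond to a neutrophil or platelet count at the starts the plan schedules.

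**Working it through.** The plan gives no figure on this point to reproduce. The check sets the rules side by side and then does day arithmetic.

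**Step 1: the rules compared**

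| Place | When it applies | Consequence of a hematologic DLT |
|---|---|---|
| 7.1.5, opening | DLT during the preceding infusions | Stop |
| 7.1.5, block-start list | DLT present on the start day | Delay; dosing possible next day or at 1 week |
| 7.3, note | No time limit | Stop |
| 7.5 | No time limit | Stop |
| 8.2, table | By Day 29; not limited to infusion days | Not eligible to continue |
| 10.3, note | Not limited to infusion days | Not eligible to continue |

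Stop appears five times and delay once. Assigning the opening rule to infusion days and the list to the 72-hour rest does not resolve the conflict, because 7.3, 7.5, 8.2 and 10.3 cover the rest period too.

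**Step 2: which items can be present at a block start**

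Inputs: planned starts on Day 8 and Day 15 (8.1); a delay of 0, 1 or 7 days per block (7.1.5); a count threshold of at least 29 days (7.2.1).

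With d2 and d3 as the delays before Blocks #2 and #3:
- Block #2 day = 8 + d2
- Block #3 day = 8 + d2 + 7 + d3
- Elapsed days since first dose = day − 1

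| d2 | d3 | Block #2 day (elapsed) | Block #3 day (elapsed) | 29 elapsed days reached? |
|---|---|---|---|---|
| 0 | 0 | 8 (7) | 15 (14) | No |
| 1 | 1 | 9 (8) | 17 (16) | No |
| 0 | 7 | 8 (7) | 22 (21) | No |
| 7 | 0 | 15 (14) | 22 (21) | No |
| 7 | 7 | 15 (14) | 29 (28) | No; calendar Day 29 only |

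The neutrophil and platelet items therefore cannot be met at any planned or once-delayed start. Only two successive 1-week delays bring Block #3 to calendar Day 29, and even then only 28 days have elapsed.

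**Step 3: item count**

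- AML: 3 items, of which 2 have the 29-day minimum and 1 (bleeding) has none.
- MDS/mast cell: 4 items, of which 2 have the minimum and 2 (bleeding, anemia) have none.
- Total: 3 + 4 = 7 items. With the minimum: 2 + 2 = 4. Without: 1 + 2 = 3.

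The stop/delay conflict is reachable for those 3. The block-start line is inert for the other 4 at planned and once-delayed starts.

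**Step 4: an example**

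An MDS patient has treatment-related Grade 4 anemia, not explained by the disease, on Day 8, and it has resolved by Day 9. Under 7.3 and 7.5 treatment is over. Under the block-start list the patient waits one day and, if the other criteria and the clinician's judgment allow, may start Block #2 on Day 9.

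**Step 5: what follows in the analysis**

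- If the patient is stopped at Block #2, 12.1 calls for replacement. If delayed, the patient stays in the response count only after completing Block #2; delay alone is not enough.
- At Block #3 the patient has already completed Blocks #1 and #2, so the replacement sentence is not triggered. Exposure is affected, as is membership of the optional subgroup receiving all 3 blocks.
- Section 12.1 keeps anyone who completed Block #1 evaluable for DLTs, so the event enters the CRM on either reading.

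**The case against.** The best defense is that the list sets conditions a patient must satisfy, and does not license dosing someone already disqualified. The disqualification comes first in 7.1.5 and is repeated in four other places. A site can comply with every line by stopping, and even the next-day restart needs the clinician's agreement. Part of this stands: a site reading the whole protocol would more likely stop. It does not remove the conflict, because the list names its own consequence, which is delay with a route back to dosing, and applies it to a hematologic DLT under the same definition.

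A second defense is that the line is meant for patients who fit the hematologic description without an event attributed to treatment. Relatedness does matter: unrelated bleeding or anemia is not a DLT. But the line points to the 7.2.1 definition, which includes relatedness, so this reading would need different wording.

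Third, many of these patients have Grade 4 counts at baseline, as 7.2.1 explains, so having no acute count threshold may be deliberate. That is fair. The point is that the line as written cannot act on counts at those starts, not that a threshold is required.

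A reader might also infer more than the documents support:
- *That the MTD estimate is distorted.* A patient who completed Block #1 remains evaluable for DLTs, so the event counts either way.
- *That delayed patients gain access to re-treatment.* Sections 4, 7.3 and 7.4 bar re-treatment after a DLT-equivalent toxicity on either reading.
- *That the count items can never be reached.* A double delay puts Block #3 on calendar Day 29.
- *That every patient is affected.* The rule covers all patients, but the conflict needs a related, duration-free hematologic DLT that is present on the start day and then clears.

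**Conclusion.** The contradiction is real and lies in the current text. Section 7.1.5 gives two consequences for the same hematologic DLT, and the delay route also conflicts with 7.3, 7.5, 8.2 and 10.3. The conflict is reachable for 3 of the 7 listed items: uncontrollable bleeding in both disease groups and unexplained Grade 4 anemia in MDS/mast cell disease, each only if treatment related. For the other 4 the block-start line has no effect at planned or once-delayed starts.

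The consequence is limited. It can change a patient's exposure and, at the Block #2 start, whether that patient is replaced or can remain in the Phase II response count. It does not alter DLT counting for patients who completed Block #1 or eligibility for re-treatment. The documents give no rates for these events, so the number of patients affected cannot be estimated. The conclusion assumes that the list means what it says about delay, and that the 29 days run from the first dose of the course. It merits correction at the next amendment.

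**What to change.** Reconcile the block-start list in 7.1.5 with that section's opening sentence and with 7.3, 7.5, 8.2 and 10.3, so that each hematologic event has one consequence. State explicitly what applies to events in the 72-hour rest. If a hematologic condition for starting a block is intended, word it so that it can be assessed on the block-start day. The consequence and any threshold are for the clinical team to decide. Once that is settled, check that the replacement and evaluability wording in 12.1 agrees with it.

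The cost is amendment wording and a clinical decision on intent. No extra tests are needed, since 8.1 already schedules a CBC on each block-start day.

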**Dose Finding Phase I Component:**

Each patient receives GTB-3550 TriKE at the assigned CI dose for 3 sets (infusion block #1, #2, and #3) of 4 consecutive 24 hours infusions separated by a 72 hour rest.

Dose Level	GTB-3550 TriKE Dose daily continuous infusion (CI) dose ( $\mu\text{g/kg/day}$ )
1	5
2	10
3	25
4	50
5	100
6	150
7	200

The phase I component uses a continual reassessment method (CRM). Patients are enrolled in cohorts of 2 beginning at Dose Level 1. A minimum of 1 week must separate each patient. Both patients within each cohort must reach Day 28 (end of the DLT assessment period) prior to enrollment of a subsequent cohort. The study statistician assigns each new cohort of 2 patients to the most appropriate dose level based on updated toxicity probabilities. As enrollment proceeds, each cohort will be assigned to an increased, decreased or equivalent dose level based on prior data in the trial. Enrollment continues until the study sample reaches evaluable 30 patients. At that time the maximum tolerated dose (MTD) for the Phase II component will be identified.

**Dose Limiting Toxicity (DLT)** is defined as any related treatment emergent toxicity within 28 days (as assessed on Day 29) of the first dose of TriKE with the exception of those that are clearly and incontrovertibly due to extraneous causes for the following criteria based on CTCAE v5:

- Any Grade 4 or 5 non-hematologic events
- Grade 3 non-hematologic adverse events lasting more than 72 hours, except the following:
  - Non-sustained (< 7 days) Grade 3 liver function tests (ALT/AST, alkaline phosphatase, total or direct bilirubin) abnormalities in the absence of clinical signs of hepatic dysfunction (lethargy, confusion, anorexia, pruritus or tremors).
  - Non-sustained Grade 3 QTc prolongation (< 72 hours) in the absence of cardiac arrhythmia
  - Grade 3 electrolyte disturbances that resolve, with or without intervention, to < Grade 2 levels within 72 hours
  - Grade 3 fatigue
  - Grade 3 anorexia
  - Grade 3 fever
  - Grade 3 infection

- Hematologic Toxicity - Given that AML and MDS inherently leads to low neutrophils and platelets, standard grading cannot be used as many of these patients technically meet criteria for “grade 4” neutropenia or thrombocytopenia at baseline. Thus, the hematologic DLTs are listed below:
  - AML:
    - Grade 4 neutrophil count (<500/ $\mu$ L) lasting  $\geq$  29 days from start of cycle in absence of evidence of active leukemia

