## 7.2 GTB-3550 TriKE Dose Levels

### 7.2.1 Dose Finding Component (Phase I)

The 1st two patients will be assigned dose level 1. The study statistician (UMN biostatistician [name] or designee) will assign each new cohort of 2 patients to the most appropriate dose level based on updated toxicity probabilities. Both patients within a dose cohort must reach Day 28 (end of the DLT assessment period) prior to enrollment of a subsequent cohort. Enrollment continues until 30 evaluable patients are accrued.

Dose Level	GTB-3550 TriKE Dose daily continuous infusion (CI) dose ( $\mu$ g/kg/day)
1	5
2	10
3	25
4	50
5	100
6	150
7	200

**Dose Limiting Toxicity (DLT)** is defined as any of the following related treatment emergent toxicity with the exception of those that are clearly and incontrovertibly due to extraneous causes within 28 days (**as assessed on Day 29**) of the first dose of TriKE for the following criteria based on CTCAE v5:

- Any Grade 4 or 5 non-hematologic events
- Grade 3 non-hematologic adverse events lasting more than 72 hours, except the following:
  - Non-sustained (< 7 days) Grade 3 liver function tests (ALT/AST, alkaline phosphatase, total or direct bilirubin) abnormalities in the absence of clinical signs of hepatic dysfunction (lethargy, confusion, anorexia, pruritus or tremors).
  - Non-sustained Grade 3 QTc prolongation (< 72 hours) in the absence of cardiac arrhythmia
  - Grade 3 electrolyte disturbances that resolve, with or without intervention, to < Grade 2 levels within 72 hours
  - Grade 3 fatigue
  - Grade 3 anorexia
  - Grade 3 fever
  - Grade 3 infection
- Hematologic Toxicity - Given that AML and MDS inherently leads to low neutrophils and platelets, standard grading cannot be used as many of these patients technically meet criteria for "Grade 4" neutropenia or thrombocytopenia at baseline. Thus, the hematologic DLTs are listed below:
  - AML
    - Grade 4 neutrophil count (< 500/ $\mu$ L) lasting  $\geq$  29 days from start of cycle in absence of evidence of active leukemia
    - Grade 4 platelet count (< 25,000/ $\mu$ L) lasting  $\geq$  29 days from start of cycle in absence of evidence of active leukemia
- Any clinically significant bleeding that is not controllable with transfusion support
  - MDS/mast cell diseases:
    - Grade 4 neutrophil count (<500/ $\mu$ L) lasting  $\geq$  29 days from start of cycle in absence of evidence of active MDS/mast cell disease

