## 8 Schedule of Patient Activities

Scheduled evaluations after screening may be performed  $\pm 1$  day from the targeted date through Day 29; unless otherwise noted. A disease reassessment will occur between Days 21 and 42. A  $\pm 7$  day window is permitted for the end of treatment (EOT) visit. If a patient discontinues treatment before receiving all 3 blocks, subsequent time points are adjusted to maintain timing (i.e. Day 22 is moved to 1 week after the start of the last block).

In addition, targeted days may be altered as clinically appropriate. Follow-up visits are per standard of care with disease status and survival status abstracted from the medical record.

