## 10.2 Event Documentation

Event monitoring and documentation begins with the 1st dose of TriKEs.

For the purposes of this study, selected expected adverse events will be assessed using the Targeted Toxicity Worksheet ([Appendix VI](#)) and any unexpected events will be collected at the following time points in relation to the GTB-3550 TriKE infusions through Day 29:

- Prior to the infusion start of each 24 hour infusion (i.e. Day 1, 2, 3, 4, and Day 8, 9, 10, 11, and Day 15, 16, 17, 18)
- At the end of the final infusion of each block (i.e. Day 5, Day 12, Day 19)
- Day 22
- Day 29

At each time point, the worst grade of the targeted toxicity since the last assessment or the previous 24 hours (whichever is shorter) will be recorded in addition to any unexpected toxicities felt at least possibly related the study treatment.

If a patient discontinues study therapy early or otherwise does not receive treatment as planned, the targeted toxicity assessment time points may be adjusted or eliminated; however, patients must be assessed for a minimum of 28 days from the 1st dose of study drug.

If a patient is not abiding by the standard of care study calendar ([Section 8.1](#)), collection of the corresponding targeted events (and research related samples) also may be altered or discontinued on an individual patient basis, as appropriate.

Monitoring for adverse events will end after the last targeted assessment; however, the investigator is obligated, upon knowledge of, to report any event meeting the criteria in [Section 10.5](#).

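### A one-week block delay leaves 2 days instead of 9 to observe DLTs after Block 3, because the 28-day DLT window and the cohort gate do not move with the delay

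*Combined protocol and SAP*

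**What the plan says.** **Delay.** Section 7.1.5: "The start of Block #2 or Block #3 may be delayed for up to 1 week". The reasons include treatment and non-treatment problems "or for holiday/scheduling issues". Section 7.5 ends treatment if "the patient is unable to start Block #2 or #3 within 1 week of the planned date". Neither section says whether Block 3's planned date moves when Block 2 starts late.

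**DLT window.** The study schema counts toxicity "within 28 days (as assessed on Day 29) of the first dose of TriKE". Sections 7.2.1 and 10.3 use the same 28 days.

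**Cohort gate.** Section 7.2.1: "Both patients within a dose cohort must reach Day 28 (end of the DLT assessment period) prior to enrollment of a subsequent cohort". The synopsis and Sections 4 and 12.1 repeat it. None makes it conditional on Block 3 having been given or followed.

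**Planned calendar.** Section 10.2 places the pre-infusion assessments on "Day 1, 2, 3, 4, and Day 8, 9, 10, 11, and Day 15, 16, 17, 18" and the block ends on "Day 5, Day 12, Day 19".

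**Re-timing.** Section 8: "If a patient discontinues treatment before receiving all 3 blocks, subsequent time points are adjusted to maintain timing". Section 7.5 does the same, keeping the Day 22 and Day 29 activities at 1 and 2 weeks from the start of the final block. Both rules are written for patients who stop early, not for patients whose blocks are late.

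**Target.** Section 12.1 defines the MTD for the course of three weekly blocks, as the dose closest to a 20% DLT rate. It makes a patient evaluable for DLT once Block 1 is complete.

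**The concern.** Treatment can move while the window that scores it stays fixed. The CRM in Section 12.1 takes each patient as DLT or no DLT and gives no reduced weight to incomplete observation. A patient whose Block 3 is late can therefore count as a full non-DLT for three blocks, with little or no observation after the third.

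The error runs one way, toward under-counting DLTs. It may also be selective. Fever, raised liver tests and low blood pressure are among the findings that hold a block under Section 7.1.5, so patients with possible early toxicity may be those who lose follow-up. With cohorts of two, one unrecorded DLT can change the next dose assignment.

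**Working it through.** **1. Reproduce the planned calendar.** A block is 4 × 24 h = 96 h followed by 72 h of rest, so block starts are 7 days apart. Let d2 and d3 be the delays of Blocks 2 and 3 in days.

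- Block 3 start = 15 + d2 + d3
- Block 3 end = 19 + d2 + d3
- Days of window left = 28 − end

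With no delay the blocks run Days 1-5, 8-12 and 15-19, which matches Section 10.2.

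**2. Apply the delays.**

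| Total delay | Block 3 | Block 3 hours inside the window | Days left to Day 28 |
|---|---|---|---|
| 0 | Days 15-19 | 96 of 96 | 9 |
| 7 (one slip) | Days 22-26 | 96 of 96 | 2 |
| 14 (both slip) | Days 29-33 | 0 of 96 | none |

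The last row needs Block 3's planned date to move with Block 2. If that date stays at Day 15, the latest start is Day 22 and the middle row is the worst case. Section 7.3.3 adds a complication. It allows liver tests two weeks to recover before the next block, against the 1-week limit in Sections 7.1.5 and 7.5. If that permits a 14-day delay of one block, Block 3 would also start on Day 29.

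**3. DLTs defined by duration, after one slip.**

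- Grade 3 non-hematologic event lasting more than 72 h: onset at the end of Block 3 gives 26 + 3 = Day 29, so the duration cannot be shown by Day 28. Undelayed, 19 + 3 = Day 22.
- Grade 3 liver-test rise without clinical signs (exempt if under 7 days), or tumor lysis syndrome unresolved at 7 days: 22 + 7 = Day 29, so onset after Day 22, the first day of the delayed Block 3, cannot be shown to reach 7 days at the Day 29 assessment. Undelayed, even onset at the end of Block 3 gives 19 + 7 = Day 26.

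The ±1-day visit window in Section 8 shifts these limits by a day at most.

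**4. Illustration of size when Block 3 is wholly outside.** Assume a true three-block DLT risk of 20% and let w be Block 3's share of the cumulative hazard. Risk seen = 1 − (1 − 0.20)^(1 − w).

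- w = 0.10: 1 − 0.8^0.9 = 18.2%
- w = 1/3: 1 − 0.8^(2/3) = 13.8%
- w = 0.50: 1 − 0.8^0.5 = 10.6%

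These are per-patient figures. The trial-level effect depends on how often delays occur, which the documents do not give.

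**5. Can one unrecorded DLT move the dose?** I used the Section 12.1 model: DLT probability = skeleton^exp(α), with α normal, mean 0, variance 0.5. The skeleton was 3, 5, 7, 10, 14, 17 and 20%. Section 12.1 lists six skeleton values; using its 17% for the added level as the seventh is my assumption. I assumed two patients at each of levels 1-6 and no DLT below level 6.

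- Two DLTs recorded at level 6: posterior mean DLT risk is 20.3% at level 5 and 23.4% at level 6, so level 5 is recommended.
- One recorded: 15.9% at level 6 and 18.6% at level 7, so level 7 is recommended.

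Plugging in the posterior mean of α gives the same two recommendations. The effect is not universal. At level 3, with no earlier DLT, one or zero recorded DLTs both lead to level 4 once the no-skipping rule is applied.

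**The case against.** **A reader might infer that any delayed patient receives Block 3 partly or wholly outside the window.** The calendar does not support that. After one slip all 96 hours are inside, and what is lost is follow-up. If the only choices in Section 7.1.5 are a next-day start or a full week, possible total delays are 0, 1, 2, 7, 8 or 14 days. Of these, only the double week leaves the window, and partial overlap never occurs.

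**A reader might take it as given that both blocks may slip and the delays add up.** Section 7.1.5 names one block or the other, and Section 7.5 counts from a planned date it does not define after a delay. The double slip is a possible reading, not a stated rule.

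**A reader might conclude that late toxicity goes unobserved.** It does not. Section 4 continues toxicity assessment through Day 60. Section 8 allows targeted days to be altered. Section 10.2 allows toxicity time points to be adjusted when treatment does not go as planned, and its 28 days of assessment is a minimum. But these provisions are discretionary or general, and none makes a later event a DLT or enters it in the CRM.

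**Low oxygen saturation is not a good example of selective delay.** Section 7.3.5 makes Grade 3 hypoxia a DLT that ends treatment, so such a patient is already counted.

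**The duration argument has limits.** Grade 4 non-hematologic events are DLTs whatever their duration. Section 10.3 asks that toxicity occur within 28 days, which could be read as fixing onset only. The Day 29 assessment wording in the schema and Section 7.2.1 leaves this open.

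**A common fixed window was deliberate.** The revision history says DLT assessments were aligned to Day 29 so that cohorts could progress together. Phase II also monitors Grade 4-5 toxicity to Day 42 and treatment-related mortality to Day 60. The first explains the window but does not address delayed blocks. The second begins only after the dose has been chosen.

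**Conclusion.** The concern holds in a limited form. Followed as written, one permitted 1-week slip cuts DLT observation after Block 3 from 9 days to 2 and prevents timely confirmation of some duration-based DLTs, while the patient can still count as a full non-DLT. This needs no disputed reading of the delay rule. If both starts slip a full week and Block 3's planned date moves with Block 2, the whole of Block 3 falls after the window has closed and after the next cohort may have opened.

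The direction is toward under-counting DLTs, but the size cannot be stated. The range of about 18% to 11% against a true 20% rests on assumed hazard shares and applies only to a patient whose Block 3 is wholly outside. The level 5 versus level 7 result shows that one missed DLT can matter in a particular data pattern. It does not show that it usually would.

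**What to change.** Reconcile the passages on block delay, DLT window and cohort gate, leaving the delay rule itself unchanged.

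1. In Sections 7.1.5 and 7.5, state whether Block 3's planned date moves when Block 2 is late, and reconcile both with the recovery period in Section 7.3.3.
2. In the synopsis, schema and Sections 4, 7.2.1, 10.3 and 12.1, run DLT observation for CRM scoring, and the cohort gate, to the later of the present 28-day window and 14 days from the start of the last block given. Undelayed patients already have this: 15 + 14 = Day 29.
3. In Sections 8 and 10.2, tie the Day 22 and Day 29 assessments of delayed patients to the actual start of the final block, as is already done for early stoppers.
4. Align the Section 5.3 requirement to stay near the center, which now runs through at least Day 29.

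The cost is wording plus waiting time in affected cohorts only. After one slip the period ends on 22 + 14 = Day 36, one week later than now. After two it ends on 29 + 14 = Day 43, two weeks later. Affected patients would also have later visits and a longer stay near the center. Undelayed cohorts are not slowed.
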